9.4 Statistical Analyses

Below is a description of planned statistical analyses. Further details are presented in the Statistical Analysis Plan (SAP).

9.4.1 General Considerations

All statistical analyses will be conducted using SAS, Version 9.4 or later. Baseline characteristics will be summarized by treatment arm. For continuous measures the mean and standard deviation (SD) will be summarized. Categorical variables will be described by the proportion in each category. In addition, 95% confidence intervals (CIs) will be computed as indicated.

All the categorical variables including the primary endpoint will be summarized by treatment with the numbers and percentages of the participants. Treatment difference will be tested using a Cochran–Mantel–Haenszel test stratified by 1) country and 2) participant's clinical status at Baseline. For the categorical endpoints, relative risk and its 95% CI will be presented.

All of the continuous variables, including the changes from Baseline, will be summarized by treatment with the means, SD, medians and the ranges. The mixed model with repeated

measurements /analysis of covariance model with treatment, country, participant's clinical status at Baseline and visit as the model term, and Baseline value as the covariate will be used to test for the significance of the treatment difference. Least square means, standard errors, 95% CIs and p-values will be presented.

Time to event endpoints will be analyzed using the Cox Proportional Hazard model with treatment, participant's clinical status at Baseline and country as the model term. The hazard ratio of RESP301+SOC versus SOC will be presented along with 95% CI and p-value from the model. The Kaplan-Meier curves of the time to events will be presented by treatment for each applicable endpoint.

Handling of missing data

If participants are discharged from the hospital prior to Day 14 due to improvement of the clinical status and their status on Day 14 cannot be obtained, their status on Day 14 for the primary endpoint will be imputed with the status on the day of discharge. Depending on the reasons for missing data on the primary endpoint up to Day 14, additional sensitivity analyses will be performed. Further details on handling on missing data will be provided in the SAP.

9.4.2 Primary Endpoint

The primary endpoint is the proportion of participants who progress to level >4 of the modified WHO ordinal scale due to COVID-19 by Day 14.

9.4.3 Secondary Endpoint(s)

The key secondary endpoints are:

1. Change from baseline on the modified WHO ordinal scale at each visit up to Day 28
2. Change in room air SpO₂ from baseline over time
3. Change in NEWS 2 symptom score from baseline over time
4. Time to improvement to a lower level (<4) of the modified WHO ordinal scale
5. Time to progression to a higher level (>4) of the modified WHO ordinal scale

Additional secondary endpoints are:

1. Time to hospital discharge
2. Incidence of mortality by Day 28

9.4.4 Tertiary/Exploratory Endpoint(s)

CCI

- CCI

9.4.5 Other Safety Analyses

All safety analyses will be performed on the Safety Population.

1. Safety and tolerability assessed by clinical safety laboratory measurements, physical examinations, vital signs, concomitant medications; cumulative incidence of AEs, SAEs and severe AEs
2. Incidence of participants unable to tolerate nebulization due to:
 - Reduction in SpO₂ to < 90%, unless well clinically tolerated according to Investigator's opinion
 - Other clinical signs of intolerance according to Investigator's opinion
3. Incidence of clinical bronchial hyper-responsiveness related to nebulization

9.4.5.1 Adverse Events

Adverse Events will be coded using the MedDRA coding dictionary.

The number and percentage of participants with any AE, any related AE, any SAE, any related SAE, any severe AE, and related severe AE as well as the total number of events for each category will be summarized. The number of deaths due to an AE, hospitalization due to an AE, and study discontinuation due to an AE will be summarized.

The number and percentage of participants with an AE, as well as the total number of AEs, will be summarized by SOC and preferred term. This tabulation will be repeated for related AEs, SAEs, related SAEs, severe AEs, and related severe AEs.

All AEs will be provided in patient listings. Patient listings of AEs causing discontinuation of study medication, AEs leading to death, SAEs, related AEs, and severe AEs will be produced.

9.4.5.2 Clinical Laboratory Evaluation

Baseline is defined as the last non-missing value obtained at the screening visit and prior to the first exposure to study drug. Actual values and changes from Baseline clinical laboratory tests

will be summarized by study day. If more than one laboratory result is reported per study visit per parameter, the last non-missing result will be selected for change from Baseline analysis.

Laboratory test results will be classified according to the reference ranges and clinical significance as determined by the Investigator. The number of participants with a non-missing result, the number and percentage of participants with a clinically significant result less than the lower limit of normal, non-clinically significant result more than the ULN, and clinically significant result more than the ULN will be summarized by study visit. If more than one laboratory result is reported per study day per parameter, the result yielding the most severe classification will be selected for analysis.

Categorical laboratory test results (urinalysis excluding pH) will be summarized by study visit. If more than one laboratory result is reported per study day per parameters, the result yielding the most severe classification will be selected for analysis.

Participants who had urine pregnancy test at screening and the results will be listed.

Participants with clinically significant abnormal laboratory test results will be listed. This listing will include all results of the laboratory parameter that was abnormal and determined to be clinically significant by the Investigator for a participant across study visit.

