9.4.5.3 Vital Signs

Baseline is defined as the last non-missing value obtained in screening and prior to the first exposure to study drug. Actual values and changes from Baseline in vital signs will be summarized by study day and study time point. All vital sign data will be presented in patient listings.

Vital sign values will be classified according to the clinical significance as determined by the Investigator. The number of participants with a non-missing result, the number and percentage of participants with a non-clinically significant result, and clinically significant result will be summarized by study visit and study time point. If more than one vital sign result is reported per study day and study time point per parameter, the result yielding the most severe classification will be selected for analysis.

Participants with clinically significant vital sign values will be listed. This listing will include all results of the vital sign parameter that was determined by the Investigator to be clinically significant for a participant across study time points.

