8.2.4 Clinical Safety Laboratory Assessments

Refer to Appendix 3 for the list of clinical laboratory tests to be performed and to the SoA (Table 1-1) for the timing and frequency.

The Investigator must review the laboratory report, document this review, and record any clinically relevant changes occurring during the study in the AE section of the CRF. The laboratory reports must be filed with the source documents. Clinically relevant abnormal laboratory findings are those which are not associated with the underlying disease, unless judged by the Investigator to be more severe than expected for the participant's condition.

All laboratory tests with values considered clinically abnormal during participation in the study or within 4 days after the last dose of study intervention should be repeated until the values return to normal or baseline or are no longer considered clinically significant by the Investigator or Medical Monitor.

- If such values do not return to normal/baseline within a period of time judged reasonable by the Investigator, the etiology should be identified, where possible, and the Sponsor notified.

- All protocol-required laboratory assessments, as defined in Appendix 3, must be conducted in accordance with the Laboratory Manual and the SoA (Table 1-1).
- If laboratory values from laboratory assessments not specified in the protocol and performed at the institution's local laboratory result in the need for a change in participant management or are considered clinically relevant by the Investigator (e.g., are considered to be an SAE or an AE), then the results must be recorded in the CRF.

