9.4.5.2 Clinical Laboratory Evaluation

Baseline is defined as the last non-missing value obtained at the screening visit and prior to the first exposure to study drug. Actual values and changes from Baseline clinical laboratory tests will be summarized by study day. If more than one laboratory result is reported per study visit per parameter, the last non-missing result will be selected for change from Baseline analysis.

Laboratory test results will be classified according to the reference ranges and clinical significance as determined by the Investigator. The number of participants with a non-missing result, the number and percentage of participants with a clinically significant result less than the lower limit of normal, non-clinically significant result more than the ULN, and clinically significant result more than the ULN will be summarized by study visit. If more than one laboratory result is reported per study day per parameter, the result yielding the most severe classification will be selected for analysis.

Categorical laboratory test results (urinalysis excluding pH) will be summarized by study visit. If more than one laboratory result is reported per study day per parameters, the result yielding the most severe classification will be selected for analysis.

Participants who had urine pregnancy test at screening and the results will be listed.

Participants with clinically significant abnormal laboratory test results will be listed. This listing will include all results of the laboratory parameter that was abnormal and determined to be clinically significant by the Investigator for a participant across study visit.

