9.4.5.3 Vital Signs

Baseline is defined as the last non-missing value obtained in screening and prior to the first exposure to study drug. Actual values and changes from Baseline in vital signs will be summarized by study day and study time point. All vital sign data will be presented in patient listings.

Vital sign values will be classified according to the clinical significance as determined by the Investigator. The number of participants with a non-missing result, the number and percentage of participants with a non-clinically significant result, and clinically significant result will be summarized by study visit and study time point. If more than one vital sign result is reported per study day and study time point per parameter, the result yielding the most severe classification will be selected for analysis.

Participants with clinically significant vital sign values will be listed. This listing will include all results of the vital sign parameter that was determined by the Investigator to be clinically significant for a participant across study time points.

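### The laboratory abnormality table in Section 9.4.5.2 leaves out low results that the Investigator does not call clinically significant, so the number of participants below the lower limit of normal cannot be obtained by arm

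*Protocol*

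**What the plan says.** Section 9.4.5.2 (Clinical Laboratory Evaluation) sets the basis of the classification: "Laboratory test results will be classified according to the reference ranges and clinical significance as determined by the Investigator". Besides the number with a non-missing result, it names the classes to be counted: "participants with a clinically significant result less than the lower limit of normal, non-clinically significant result more than the ULN", followed by "and clinically significant result more than the ULN will be summarized by study visit". The wording is the same in the current text (the version for WHO levels 3 and 4) and in the preceding protocol version in the same file.

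The section also plans two other outputs:

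- Continuous summaries: "Actual values and changes from Baseline clinical laboratory tests will be summarized by study day". Section 9.4.1 adds that continuous variables are summarized by treatment with means, SDs, medians and ranges.
- A listing: "Participants with clinically significant abnormal laboratory test results will be listed". For a participant who qualifies, it shows every result of the parameter concerned.

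The trial is open-label, as the Synopsis and Section 6.3 state.

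**The concern.** The section declares a two-way classification and then lists an incomplete set of its cells. The gap is on one side only. High results are counted whether or not they are flagged; low results are counted only when flagged. If the table is programmed as written, a participant whose only abnormality is an unflagged low value is in the denominator but in no abnormal row.

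The low side is not empty. Hemoglobin, platelets, white cells and electrolytes are required tests (Appendix 3). The schedule places the blood count in both arms at screening and on Days 1, 3, 7 and 10, and a low platelet count is itself an exclusion criterion (Section 5.3). The protocol describes the study as first-in-man (Section 2.2.3), so a low-direction signal that nobody foresaw should at least be countable. As written, the by-arm comparison of low results in this table reflects Investigator judgement made with knowledge of the arm, without a count of the values beside it.

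**Working it through.** The plan gives no figure to reproduce. The check is to enumerate the classes and then see whether any other planned output supplies the missing one.

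**Step 1: classes implied and classes listed.** Two directions × two significance levels = 4 out-of-range classes.

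| | Not clinically significant | Clinically significant |
|---|---|---|
| Below LLN | not listed (NL) | listed (CL) |
| Above ULN | listed (NH) | listed (CH) |

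Listed: 3 of 4.

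**Step 2: what can be rebuilt.** For one parameter at one visit in one arm, let N be the participants with a non-missing result and W those within range. Section 9.4.5.2 takes the most severe classification when there are several results on a day, so I treat the classes as exclusive:

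N = W + NL + CL + NH + CH.

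The table reports N, CL, NH and CH.

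- Total above ULN = NH + CH. Both terms are reported, so it is known.
- Total below LLN = NL + CL. Only CL is reported.
- Remainder = N − CL − NH − CH = W + NL. Unflagged low results are merged with normal results and cannot be separated.

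All the table says about the low total is that it lies between CL and N − NH − CH.

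**Step 3: whether another output supplies NL.**

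- The listing is limited to participants with a clinically significant result. A participant whose low values of a parameter are never flagged does not appear for that parameter.
- The adverse event route (Section 10.4.1) takes in an abnormal laboratory result when the Investigator considers it clinically significant. Section 8.2.4, on what is recorded in the adverse event section of the case report form, says "Clinically relevant abnormal laboratory findings are those which are not associated with the underlying disease", with an exception for findings judged more severe than expected. This route also depends on Investigator judgement.
- The continuous summaries do not depend on the flag. They show location, spread and the extreme values by arm, but not how many participants were below LLN.

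Every planned count of participants with low laboratory results therefore passes through the flag; the continuous summaries do not.

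**The case against.** The strongest reply is that this is one dropped phrase in a descriptive safety table. The by-arm ranges would show an extreme low hemoglobin or platelet value whatever the flag. The named laboratory risk, methemoglobin, is a high-side result with both rows present and a discontinuation threshold of 3% in Section 7.1. The liver criteria in that section are also fixed multiples of the ULN or a fixed INR, with mandatory reporting. Section 9.4 defers further detail to the SAP, which is not shown and may restore the row. All of this limits the consequence. It does not remove the point, because Section 9.4.5.2 does not leave the classes to the SAP: it names them, and the list disagrees with the classification stated just before it.

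A reader might infer three stronger things that the documents do not support.

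- *That abnormal vital signs are likewise counted only when flagged.* Section 9.4.5.3 does classify by significance alone: "Vital sign values will be classified according to the clinical significance as determined by the Investigator". But it counts both groups ("the number and percentage of participants with a non-clinically significant result, and clinically significant result will be summarized"), summarizes actual values and changes, and lists all vital-sign data. What is left is a small ambiguity: the text does not say whether the row for results that are not clinically significant also holds normal values. Fixed limits for vital signs are commonly left to the SAP.
- *That a real fall in blood counts would be hidden.* It would be missing from the unflagged part of one categorical table, while the continuous summaries would still reflect it.
- *That flagging will differ between arms in a known direction or by a known amount.* Differential flagging is plausible when the arm is known, but the documents give neither a below-LLN rate nor flagging rates. Any risk ratio built on assumed flagging rates would only return the assumption.

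**Conclusion.** The point holds for the laboratory table: 3 of 4 out-of-range classes are tabulated, and results below the LLN that are not judged clinically significant are omitted. The low total by arm cannot be recovered from the table, the listing or the adverse event data. The consequence is limited to that categorical table. The primary endpoint, the continuous laboratory summaries and the methemoglobin counts are unaffected, and no size can be given for any distortion between arms. The conclusion assumes that the table is produced as Section 9.4.5.2 words it; an SAP that restores the row would settle the matter, but the protocol text would still need to agree with it.

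**What to change.** In Section 9.4.5.2, add the fourth class: a result below the lower limit of normal that is not clinically significant. Also report by arm and visit the number and percentage of participants below LLN and above ULN regardless of the Investigator's flag, keeping the flagged counts beside them. Carry the same rows into the SAP and table shells.

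As a minor clarification, state in Section 9.4.5.3, or by reference to the SAP, whether the vital-sign row for results that are not clinically significant includes normal values.

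The cost is a wording change and a few table rows. The results and reference ranges are already part of the planned classification, so no new data are needed.

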9.4.5.3 Vital Signs

Baseline is defined as the last non-missing value obtained in screening and prior to the first exposure to study drug. Actual values and changes from Baseline in vital signs will be summarized by study day and study time point. All vital sign data will be presented in patient listings.

Vital sign values will be classified according to the clinical significance as determined by the Investigator. The number of participants with a non-missing result, the number and percentage of participants with a non-clinically significant result, and clinically significant result will be summarized by study visit and study time point. If more than one vital sign result is reported per study day and study time point per parameter, the result yielding the most severe classification will be selected for analysis.

Participants with clinically significant vital sign values will be listed. This listing will include all results of the vital sign parameter that was determined by the Investigator to be clinically significant for a participant across study time points.

9.4.5.4 Physical Examination

Abnormal physical examination findings will be listed.

9.4.6 Other Analyses

Other analyses may be added to the SAP as applicable.

9.5 Interim Analyses

Two interim analyses will be performed.

1. The first analysis will be conducted when about 60 participants (40 participants in the RESP301+SOC arm and 20 participants in the SOC arm) have completed the Day 10 assessment. The purpose of this analysis is to evaluate efficacy of RESP301 with the application of a futility criterion based on the results on SpO₂ change from baseline on Day 10. The following futility criterion will be used for this first interim analysis:

If the difference in the percentage of participants with at least a 2% improvement in SpO₂ between both treatment arms is less than 5%, benefit of RESP301 treatment is not expected. For a final decision to stop the study for futility the results on other endpoints will be considered as well.

As no other modification of the study at the time of the first interim analysis is considered, no adjustment of the alpha level is required.

2. The second interim analysis will be conducted after 150 participants (100 participants in the RESP301+SOC arm and 50 participants in the SOC arm) have completed the Day 14 assessment. The purpose of this analysis is the assessment of futility or a sample size re-estimation in case the actual results differ from the original assumptions for the power calculations of the study, related to the percentage of participants meeting the primary endpoint in the control arm and/or the relative treatment benefit achieved in the RESP301+SOC arm compared to the SOC arm.

To account for the multiple testing due to the second interim analysis an adjustment for the type I error alpha will be applied using the Haybittle-Peto approach which would spend one sided alpha=0.0005 at the second interim analysis and leave one-sided nominal alpha of 0.0249 for the final analysis. The futility criterion for the second interim analysis will be based on the conditional power (CP) for the final results based on the assumption that the remainder of the study will follow the same trend as observed in the interim analysis. If CP at the time of the second interim analysis is less than 20% consideration

will be given to stop the study for futility. At the same time sample size re-estimation will be performed to achieve 80% power at the end of the study. The methodology for the adjustment and the procedure to maintain the type I error level will be described in greater detail in the SAP.

Detailed information, including the boundaries futility and characteristics for the sample size re-estimation at the time of the interim analyses will be provided in the SAP and Data Monitoring Committee (DMC) Charter. Further details are also provided in Appendix 5.

9.6 Data Monitoring Committee (DMC)

An IDMC will be responsible for closely reviewing the safety and efficacy data from the interim analyses and for providing their recommendations on continuation of the study. The IDMC will meet to review after 10 and 20 participants have completed as well as at the time of the interim analyses (ie, after 60 and 150 participants have completed; see Section 9.5).

Due to the urgency of the pandemic, if participants become eligible for the study during the IDMC review of the first 10 participants then they may be recruited. However, their administration of RESP301 will be staggered in the same way as for the first 10 participants (see also Section 6.1). Once the IDMC review has been completed, and provided there are no safety concerns, further recruitment will continue as per protocol. The Sponsor and CRO confirm that the report from the IDMC will be sent in a timely manner to all participating sites and investigators.

The detailed procedures and criteria of the interim analyses will be described in the DMC Charter.

10 Supporting Documentation and Operational Considerations

